			Frequency	XXXXXXX
			Given for AE or MH?	XXXXXXXXXXXXXXXXXXXX AE # XX (or MH # XX)

ATC=Anatomical therapeutic class

Source: list SAS datasets used to create listing

SAS X.Y

DDMONYYYYTHH:MM
program_name

Note to programmer: If medication is ongoing, put ONGOING in stop row. Do not split an medication across pages. Insert a page break between subjects. Values for category column are: CONCOMITANT; SURGICAL/ANESTHESIA; NON-MEDICATION; PRIOR. Use this template for the following listings:

Listing 16.2-12.2: Concomitant Medications - Randomized Subjects

Pacira Pharmaceuticals
Listing 16.2-13: Medical/Surgical History - Randomized Subjects
Treatment: TTTTTT

Protocol: 404-C-201

Date						
Site	Subject	Start	Stop	Number	Classification	Term
XXX	XXX-YYYY	DDMONYYYY	DDMONYYYY	X	System Organ Class: Preferred Term: Verbatim:	

Source: list SAS datasets used to create listing
SAS X.Y

DDMONYYYYTHH:MM
program_name

Note to programmer: If ongoing put ONGOING in stop date column.

Pacira Pharmaceuticals
Listing 16.2-14: Informed Consent - All Subjects
Treatment: TTTTTT

(Page X of Y)

Protocol: 404-C-201

Site	Subject	Subject Initials	Date		Protocol Version	Met Criteria	
			Screening Visit	Signed Consent		Inclusion	Exclusion
XXX	XXX-YYYY	ABC	DDMONYYYY	DDMONYYYY	AMENDMENT 2	YES	YES

Source: list SAS datasets used to create listing
SAS X.Y

DDMONYYYYTHH:MM
program_name

Pacira Pharmaceuticals
Listing 16.2-15.1: Subject Eligibility - All Subjects
Treatment: TTTTTTTTTTTTTT

Protocol: 404-C-201

Site	Subject	Date of		
		Informed Consent	Eligibility Assessment	Criteria Failed
XXX	XXX-YYYY	DDMONYYYY	DDMONYYYY	
XXX	XXX-YYYY	DDMONYYYY	DDMONYYYY	
XXX	XXX-YYYY	DDMONYYYY	DDMONYYYY	
XXX	XXX-YYYY	DDMONYYYY	DDMONYYYY	Inclusion: 1, 4 Exclusion: 8, 10, 12

Source: list SAS datasets used to create listing
SAS X.Y

DDMONYYYYTHH:MM
program_name

Note to programmer: If subject was not randomized treatment should be 'NOT RANDOMIZED'. Criteria Failed may take any or all of the following values: Inclusion 1, 2, 3, 4 or 5 and Exclusion 1 through 12. Insert a page break after each treatment group.

Pacira Pharmaceuticals
(Page 1 of 2)
Listing 16.2-15.2: Subject Eligibility - Inclusion/Exclusion Criteria
Inclusion/Exclusion Criteria

Protocol: 404-C-201

- Inclusion 1 Male or female, ≥ 18 years of age at screening.
- Inclusion 2 Scheduled to undergo elective unilateral open TKA under general, spinal, or regional anesthesia.
- Inclusion 3 American Society of Anesthesiology (ASA) physical status 1, 2, or 3.
- Inclusion 4 Female patient must be surgically sterile; or at least 2 years postmenopausal; or have a monogamous partner who is surgically sterile; or practicing double-barrier contraception; or practicing abstinence (must agree to use double-barrier contraception in the event of sexual activity); or using an insertable, injectable, or transdermal, contraceptive approved by the FDA for greater than 2 months prior to screening. All women of childbearing potential (ie, premenopausal without permanent sterilization) must commit to the use of an acceptable form of birth control for the duration of the study and for 30 days after completion of the study.
- Inclusion 5 Able to provide informed consent, adhere to the study visit schedule, and complete all study assessments.

Source: list SAS datasets used to create listing
SAS X.Y

DDMONYYYYTHH:MM
program_name

Pacira Pharmaceuticals
Listing 16.2-15.2: Subject Eligibility - Inclusion/Exclusion Criteria
Inclusion/Exclusion Criteria

(Page 2 of 2)

Protocol: 404-C-201

Exclusion 1 Currently pregnant, nursing, or planning to become pregnant during the study or within 30 days after study drug administration.

Exclusion 2 Planned concurrent surgical procedure (eg, bilateral TKA).

Exclusion 3 Prior open knee surgery on ipsilateral knee. Prior arthroscopy is permitted.

Exclusion 4 Patients taking a medication with a known procoagulant effect (eg, combination hormonal contraceptives, Factor IX complex concentrates or anti-inhibitor coagulant concentrates, or all-trans retinoic acid).

Exclusion 5 Contraindication or hypersensitivity to TXA.

Exclusion 6 History of thrombosis or prior VTE.

Exclusion 7 Known coagulopathy or active intravascular clotting.

Exclusion 8 Prior myocardial infarction.

Exclusion 9 Prior cardiovascular accident (stroke) or subarachnoid hemorrhage.

Exclusion 10 History of epilepsy.

Exclusion 11 Presence of an intravascular stent.

Exclusion 12 History of impaired kidney function, chronic respiratory disease, rheumatoid arthritis, coagulopathy, or loss of sensation in extremities.

Exclusion 13 Renal insufficiency as indicated by serum creatinine >upper limit of normal (by central laboratory assessment).

Exclusion 14 Anemia (Hb level <10 g/dL).

Exclusion 15 Uncontrolled anxiety, psychiatric, or neurological disorder that might interfere with study assessments.

Exclusion 16 Acquired defective color vision.

Exclusion 17 Malignancy in the last 2 years, with the exception of non-metastatic basal cell or squamous cell carcinoma of the skin or localized carcinoma in situ of the cervix.

Exclusion 18 Suspected or known history of drug or alcohol abuse within the previous year.

Exclusion 19 Body weight <50 kg (110 pounds) or a body mass index >44 kg/m².

Exclusion 20 Administration of an investigational drug within 30 days or 5 elimination half-lives of such investigational drug, whichever is longer, prior to study drug administration, or planned administration of another investigational product or procedure during the patient's participation in this study.

Source: list SAS datasets used to create listing
SAS X.Y

DDMONYYYYTHH:MM
program_name

Pacira Pharmaceuticals Listing 16.2-16: Pregnancy Test - All Subjects					(Page X of Y)	Protocol: 404-C-201		
Treatment: TTTTTTTTTT								
Site	Subject	Visit	Date	Sex	Childbearing Potential	Pregnancy Test	Result	
XXX	XXX-YYYY	Screening	DDMONYYYY	Female	YES		NEGATIVE	
		D1 Preop	DDMONYYYY					
	XXX-YYYY	Screening	DDMONYYYY	Female	NO		NOT APPLICABLE	
		D1 Preop	DDMONYYYY					
	XXX-YYYY	Screening	DDMONYYYY	Male			NOT APPLICABLE	
		D1 Preop	DDMONYYYY					

Source: list SAS datasets used to create listing
SAS X.Y

DDMONYYYYTHH:MM
program_name

Note to programmer: Possible results for screening tests are: POSITIVE, NEGATIVE, NOT DONE, or NOT APPLICABLE (if Childbearing Potential = 'NO' or Sex = 'Male').

Pacira Pharmaceuticals Listing 16.2-17: Protocol Deviations - All Subjects Treatment: TTTTTT				(Page X of Y)	Protocol: 404-C-201
Site	Subject	Start Date and Time	Protocol Deviation Coded Term	Description	Action Taken
XXX	XXX-YYYY	DDMONYYYYTHH:MM	XXXXXXXXXXXXXXXXXXXX	XXXXXXXXXXXXXXXXXXXX	XXXXXXXXXXXXXXXXXXXX

Source: list SAS datasets used to create listing
SAS X.Y

DDMONYYYYTHH:MM
program_name

Pacira Pharmaceuticals
Listing 16.2-18.1: Pharmacokinetic Concentrations - All Subjects
Treatment: DepoTXA 400 (Enrolled After Protocol Amendment 2)

Protocol: 404-C-201

Site	Subject	Date and Time of Dose				Time From Dose			
		Infusion Date	Start Time	End Time	PK Sample	Scheduled (hr)	Actual (hr)	Deviation (mins)	Concentration (ng/mL)
XXX	XXX-YYYY	DDMONYYYY	HH:MM	HH:MM	DDMONYYYYTHH:MM	0	XX	X	BLOQ
					DDMONYYYYTHH:MM	0.08	0.XX	X	XXX.X
					DDMONYYYYTHH:MM	0.25	0.XX	X	XXX.X
					DDMONYYYYTHH:MM	0.50	X	X	XXX.X
					DDMONYYYYTHH:MM	1	ND		
					DDMONYYYYTHH:MM	2	X	-X	XXX.X
					DDMONYYYYTHH:MM	4	X	X	XXX.X
					DDMONYYYYTHH:MM	6	X	X	XXX.X
					DDMONYYYYTHH:MM	8	XX	-X	XXX.X
					DDMONYYYYTHH:MM	12	XX	X	XXX.X
					DDMONYYYYTHH:MM	16	XX	X	XXX.X
					DDMONYYYYTHH:MM	24	XX	X	XXX.X
					DDMONYYYYTHH:MM	36	XX	X	XXX.X
					DDMONYYYYTHH:MM	48	XX	-X	XXX.X
					DDMONYYYYTHH:MM	60	XX	X	XXX.X
					DDMONYYYYTHH:MM	72	XX	X	XXX.X
					DDMONYYYYTHH:MM	96	XX	X	XXX.X

BLOQ=below limit of quantitation

ND=Not Done

Note: Actual time (hr) is calculated from Infusion End Time.

Source: list SAS datasets used to create listing
SAS X.Y

DDMONYYYYTHH:MM
program_name

Note to programmer: Insert a page break after each subject. If a sample was not collected - put ND in actual column under time from dose. Sort listing within subject by sample date and time.
Sort by Treatment, Enrolled Prior to Protocol Amendment 2, then Enrolled After Protocol Amendment 2, Subject, PK date/time

Pacira Pharmaceuticals (Page X of Y)
Listing 16.2-18.2: Pharmacokinetic Parameters - All Subjects
Treatment: DepoTXA 400 (Enrolled Prior to Protocol Amendment 2)

Site	Subject			Early		Late		Half-life (hr)	Lamba_z (hr)
		AUC(0-inf) (ng*hr/mL)	AUC(0-last) (ng*hr/mL)	Cmax ng/mL	Tmax (hr)	Cmax ng/mL	Tmax (hr)		
XXX	XXX-YYYY	XXXX.XX	XXXX.XX	XXX.X	XX.X	XX.X	XX.X	X.XXX	X.XXX
	XXX-YYYY	NC	XXXX.XX	XXX.X	XX.X	XX.X	XX.X	NC	NC
	XXX-YYYY	XXXX.XX	XXXX.XX	XXX.X	XX.X	XX.X	XX.X	X.XXX	X.XXX
	XXX-YYYY	XXXX.XX	XXXX.XX	XXX.X	XX.X	XX.X	XX.X	X.XXX	X.XXX
	XXX-YYYY	XXXX.XX	XXXX.XX	XXX.X	XX.X	XX.X	XX.X	X.XXX	X.XXX
YYY	XXX-YYYY	XXXX.XX	XXXX.XX	XXX.X	XX.X	XX.X	XX.X	X.XXX	X.XXX
	XXX-YYYY	XXXX.XX	XXXX.XX	XXX.X	XX.X	XX.X	XX.X	X.XXX	X.XXX
	XXX-YYYY	XXXX.XX	XXXX.XX	XXX.X	XX.X	XX.X	XX.X	X.XXX	X.XXX
	XXX-YYYY	XXXX.XX	XXXX.XX	XXX.X	XX.X	XX.X	XX.X	X.XXX	X.XXX
	XXX-YYYY	XXXX.XX	XXXX.XX	XXX.X	XX.X	XX.X	XX.X	X.XXX	X.XXX

NC=Not Calculated

Source: list SAS datasets used to create listing
SAS X.Y

DDMONYYYYTHH:MM
program_name

Note to programmer: If a parameter was not calculated - put NC in column.

Sort by Treatment, Enrolled Prior to Protocol Amendment 2, then Enrolled After Protocol Amendment 2,
Subject

Pacira Pharmaceuticals
Listing 16.2-19: Unique Adverse Events Terms and Associated Coded Terms
MedDRA Terms

SOC

Preferred Term

Verbatim(s)

SOC1

PT1.1

XXXXXXXXXXXXXXXXXXXXXXXXXXXX
XXXXXXXXXXXXXXXXXXXXXXXXXXXX
XXXXXXXXXXXXXXXXXXXXXXXXXXXX
XXXXXXXXXXXXXXXXXXXXXXXXXXXX

PT1.2

XXXXXXXXXXXXXXXXXXXXXXXXXXXX
XXXXXXXXXXXXXXXXXXXXXXXXXXXX

SOC2

PT2.1

XXXXXXXXXXXXXXXXXXXXXXXXXXXX
XXXXXXXXXXXXXXXXXXXXXXXXXXXX

Coded using MedDRA version 19.1 or higher.

Source: list SAS datasets used to create listing
SAS X.Y

DDMONYYYYTHH:MM
program_name

Note to programmer: Sort by SOC and preferred term in alphabetical order

Pacira Pharmaceuticals Listing 16.2-20: Unique Medication Terms and Associated Coded Terms Who Drug Dictionary Terms		(Page X of Y)	Protocol: 404-C-201
Preferred name	Verbatim(s)		
ACT1			
ACT2			
ACT3			
ACT4			
ATC1			
ATC1.2			
PN1.2.1	XXXXXXXXXXXXXXXXXXXXXXXXXXXX	XXXXXXXXXXXXXXXXXXXXXXXXXXXX	
PN1.2.2	XXXXXXXXXXXXXXXXXXXXXXXXXXXX		
ATC2			
ATC2.2			
ATC2.3			
ATC2.4			
PN2.2.3.4.1	XXXXXXXXXXXXXXXXXXXXXXXXXXXX	XXXXXXXXXXXXXXXXXXXXXXXXXXXX	

Coded using World Health Organization Drug Dictionary Enhanced (WHO-DD) September 2016

Source: list SAS datasets used to create listing

SAS X.Y

[figure not shown]
DDMONYYYYTHH:MM
program_name

Note to programmer: Sort by ATC1, ATC2, ATC3, ATC4 and preferred name in alphabetical order

15. TABLE OF CONTENTS FOR FIGURES

Figure 14.2-9.1: Plot of Total Blood Loss over Time by Treatment (Method 1 Hct) - Efficacy Analysis Set	105
Figure 14.2-9.2: Plot of Total Blood Loss over Time by Treatment (Method 2 Hb) - Efficacy Analysis Set	106
Figure 14.2-9.3: Plot of Total Blood Loss over Time by Treatment (Both Methods) - Efficacy Analysis Set	107
Figure 14.4-3.1: Plot of Mean (\pm SE) TXA Concentration (ng/mL) over Time by Treatment - PK Analysis Set	108
Figure 14.4-3.2: Plot of ln Mean (\pm SE) TXA Concentration (ng/mL) over Time by Treatment - PK Analysis Set	109
Figure 14.4-3.3: Plot of Individual Subject TXA Concentrations (ng/mL) over Time - PK Analysis Set	110
Figure 14.4-3.4: Plot of Mean TXA 24h AUC vs 24h Blood Loss by Method - PK Analysis Set	113

Pacira Pharmaceuticals
Figure 14.2-9.1: Plot of Total Blood Loss over Time by Treatment (Method 1 Hct) - Efficacy Analysis Set

Source: list SAS datasets used to create listing
SAS X.Y

DDMONYYYYTHH:MM
program_name

Note to programmer: Margins on the y-axis should be adjusted, but consistent for figures 14.2-9.1, 14.2-9.2, and 14.2-9.3. Use template Figure 14.2-9.1 for the following Figure:

[figure not shown]
Figure 14.2-9.2: Plot of Total Blood Loss over Time by Treatment (Method 2 Hb) - Efficacy Analysis Set

Pacira Pharmaceuticals

(Page X of Y)

Protocol: 404-C-201

Figure 14.2-9.3: Plot of Total Blood Loss over Time by Treatment (Both Methods) - Efficacy Analysis Set

Source: list SAS datasets used to create listing
SAS X.Y

[figure not shown]
DDMONYYYYTHH:MM
program_name

Pacira Pharmaceuticals

(Page X of Y)

Protocol: 404-C-201

Figure 14.4-3.1: Plot of Mean (\pm SE) TXA Concentration (ng/mL) over Time by Treatment - PK Analysis Set

[figure not shown]

Source: list SAS datasets used to create listing
SAS X.Y

DDMONYYYYTHH:MM
program_name

Pacira Pharmaceuticals (Page X of Y)
Figure 14.4-3.2: Plot of ln Mean (\pm SE) TXA Concentration (ng/mL) over Time by Treatment (for Subjects Enrolled After Protocol Amendment 2) - PK Analysis Set

Protocol: 404-C-201

Source: list SAS datasets used to create listing

DDMONYYYYTHH:MM

SAS X.Y
Pacira Pharmaceuticals

[figure not shown]
[figure not shown]
(Page X of Y)

program_name
Protocol: 404-C-201

Figure 14.4-3.3: Plot of Individual Subject TXA Concentrations (ng/mL) over Time - PK Analysis Set

[figure not shown]
[figure not shown]
Subject [contact] DepoTXA 400

[figure not shown]
Subject [contact] DepoTXA 400

Subject [contact] DepoTXA 800

[figure not shown]
Subject [contact] DepoTXA 800

Note to programmer: Margins on the y-axis should be adjusted, but consistent for figures 14.4-3.1, 14.4-3.2, and 14.4-3.3

Pacira Pharmaceuticals
Figure 14.4-3.4: Plot of Mean TXA 24h AUC vs 24h Blood Loss by Method - PK Analysis Set

Source: list SAS datasets used to create listing
SAS X.Y

DDMMONYYYYTHH:MM
program_name

Note to programmer: Set margins on the x-axis and y-axis as appropriate.

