5.2. Secondary Objectives

The secondary objectives of this study are to evaluate (1) the safety of DepoTXA, (2) the efficacy of DepoTXA (over 5 days) compared to IV TXA, and (3) a potential dose-related response to DepoTXA at 400, 800, and 1200 mg (33 mg/mL).

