6. STUDY OVERVIEW

This is a Phase 2, randomized, single-blind, active-controlled dose-ranging study in patients scheduled to undergo total knee arthroplasty (TKA). Approximately 60 subjects (15 per treatment group) are planned for enrollment. Subjects will be randomized in a 1:1:1:1 ratio to receive DepoTXA 400 mg, DepoTXA 800 mg, DepoTXA 1200 mg, or IV TXA (Cyklokapron® 1 gram).

Blood samples for PK analysis will be obtained at baseline (prior to study drug administration); at 5, 15, and 30 minutes; and at 1, 2, 4, 6, 8, 12, 16, and 24 hours after study drug administration for all treatment groups. Additional blood samples will be collected at 36, 48, 60, 72, and 96 hours after study drug administration for DepoTXA-treated subjects.

Postsurgical efficacy assessments will include measurement of blood loss (as assessed by hemoglobin [Hb] and hematocrit [Hct] levels), transfusion requirement, knee flexion, timed up-and-go (TUG) test, knee and thigh measurements, numeric rating scale (NRS_ pain scores), days to independent ambulation, and the surgical wound aspect score (SWAS).

Postsurgical safety assessments will include vital signs, neurological assessment, clinical laboratory testing (hematology, chemistry, and coagulation), 12-lead electrocardiogram (ECG), and adverse event (AE) monitoring. Subject monitoring will include, but not be limited to, changes in vision, neurologic function, or renal function; and occurrence of hematoma, wound dehiscence/disruption, surgical site infection (per Centers for Disease Control and Prevention definition), nausea, vomiting, and diarrhea.

Adverse events of special interest (AESI) include changes in color vision, venous thromboembolism or pulmonary embolism, and oliguria. If an AESI or serious AE (SAE) occurs during the study, an unscheduled PK blood sample must be collected. In addition, vital signs, the neurological assessment, and clinical laboratory tests must be conducted, as appropriate. If a subject experiences changes in color vision, an ophthalmological consultation must be ordered.

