9.8. Efficacy Analysis

No formal statistical hypothesis testing will be performed. The following endpoints will be summarized using descriptive statistics:

- Total blood loss as measured by Hb and Hct levels upon arrival at the post-anesthesia care unit (PACU) and at 6, 12, 24, 48, 72, 120 hours, and Day 7
- Incidence of transfusion (number of units/subject, number of subjects transfused)

- Time to 90° passive and active knee flexion at 24, 48, and 72 hours for patients enrolled prior to Amendment 2 and by AM/PM at 24, 48, and 72 hours for patients enrolled on Amendment 2
- Time to complete TUG test once on study day 1 (postsurgical day 0), twice a day on study day 2 (6:00 - 10:00 and 18:00 - 22:00), at hospital discharge, and on study day 7
- Change in knee and thigh measurements on the morning of postsurgical day 2 and at the day 7 follow-up visit
- NRS Pain Scores upon arrival at the PACU, at each in-hospital vital sign assessment beginning with the 48-hour assessment, and at the Day 7 follow-up visit
- Days to Independent Ambulation assessed beginning at Day 7 follow-up visit
- Surgical Wound Aspect Score (SWAS) on the morning of postsurgical day 2 and on day 7

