9.8.1. Total Blood Loss

Total loss will be calculated separately using two separate methods. The first method is based on Hct and the second method is based upon Hb. Total blood loss will be calculated at 6, 12, 24, 48, 72, 120 hours, and Day 7 postsurgery for each subject. Descriptive statistics summarizing the total blood loss will be summarized by postsurgical timepoint and treatment group for the efficacy analysis population for each method. Baseline is considered the last value measured before the surgery.

Total BV in mL will be calculated using the Nadler formula ([Nadler 1962](#)) at baseline by

$$BV_{baseline} = (a * h^3 + b * w + c)$$

where h = height (m), w = baseline weight (kg), $\{a=0.3669, b=0.03219, c=0.6041\}$ for males and $\{a=0.3561, b=0.03308, c=0.1833\}$ for females. The $BV_{baseline}$ is used in methods 1 and 2 to determine blood loss.

Method 1 ([Gibon 2013](#)):

Total RBC loss is in mL calculated by the following formula:

$$RBC_{lost} = BV_{baseline} * (Hct_{baseline} - Hct_{postop\ hour}) + BV_{transfused}$$

where $Hct_{baseline}$ is measured as the volume percentage of red blood cells in the blood at baseline, $Hct_{post-op\ hour}$ is measured as the volume percentage of red blood cells in the blood at the specified postsurgical timepoint in hours, total $BV_{baseline}$ is measured in mL, and $BV_{transfused}$ is the mL volume of blood transfused to the subject.

Method 2 ([Gao et al, 2015](#)):

Another method of calculating blood loss is presented by Gao as follows:

$$Hb_{loss} [g] = BV_{baseline} [\text{mL}] \cdot (Hb_{baseline} [\text{g/L}] - Hb_{postop} [\text{g/L}]) \cdot 0.001 [\text{L/mL}] + Hb_t [\text{g}],$$

$$Hb_t = BV_{transfused} [\text{Unit}] \cdot 52 [\text{g/Unit}], \text{ and}$$

$$RBC_{lost} [\text{mL}] = 1000 \times Hb_{loss} [\text{g}] / Hb_{baseline} [\text{g/L}],$$

where Hb_{loss} is the total loss of hemoglobin in gram, $BV_{baseline}$ is the presurgery blood volume in mL, $Hb_{baseline}$ and Hb_{postop} are the presurgery and post surgery hemoglobin concentration in g/L, Hb_t is the amount of hemoglobin transfused in gram, $BV_{transfused}$ is the banked blood transfused in Unit, and RBC_{lost} is the total volume of RBC lost. The above formulae can be simplified as

$$RBC_{lost} = \frac{BV_{baseline} * (Hb_{baseline} - Hb_{postop}) + BV_{transfused} * 52000}{Hb_{baseline}}.$$

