10. SAMPLE SIZE CALCULATION

The sample size was not based on statistical considerations.

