Note to programmer: Pharmacokinetic parameters to appear on this table are, in order of appearance, AUC(0-infinity) (hr*ng/mL), AUC(0-last) (hr*ng/mL), Global Cmax (ng/mL), Global Tmax (hr), Early Cmax (ng/mL), Early Tmax (hr), Late Cmax (ng/mL), Late Tmax (ng/mL), half-life (hr), Lambda_z (/hr).

Table 14.4-1b: Summary of Pharmacokinetic Parameters (for Subjects Enrolled After Protocol Amendment 2) - PK Analysis Set

Pacira Pharmaceuticals (Page X of Y) Protocol: 404-C-201
Table 14.4-2a: Summary of DepoTXA (ng/mL) Over Time (for Subjects Enrolled Prior to Protocol Amendment 2) - PK Analysis Set

Site: Overall		DepoTXA 400 [N=XX]	DepoTXA 800 [N=XX]	DepoTXA 1200 [N=XX]	IV TXA [N=XX]
Time	Statistic				
5 min	n	XX	XX	XX	XX
	Mean	XX.X	XX.X	XX.X	XX.X
	SD	X.XX	X.XX	X.XX	X.XX
	Minimum	XX	XX	XX	XX
	Median	XX.X	XX.X	XX.X	XX.X
	Maximum	XX	XX	XX	XX
15 min	n	XX	XX	XX	XX
	Mean	XX.X	XX.X	XX.X	XX.X
	SD	X.XX	X.XX	X.XX	X.XX
	Minimum	XX	XX	XX	XX
	Median	XX.X	XX.X	XX.X	XX.X
	Maximum	XX	XX	XX	XX
Ect.	n	XX	XX	XX	XX
	Mean	XX.X	XX.X	XX.X	XX.X
	SD	X.XX	X.XX	X.XX	X.XX
	Minimum	XX	XX	XX	XX
	Median	XX.X	XX.X	XX.X	XX.X
	Maximum	XX	XX	XX	XX

Source: list SAS datasets used to create table
SAS X.Y

DDMONYYYYTHH:MM
program_name

Note to programmer: Timepoints to appear on this table are, in order of appearance, For all subjects: at 5, 15, and 30 minutes; and at 1, 2, 4, 6, 8, 12, 16, and 24 hours after study drug administration for all treatment groups and for DepoTXA-treated subjects only: additional timepoints at 36, 48, 60, 72, and 96 hours after study drug administration.

Table 14.4-2a: Summary of DepoTXA (ng/mL) Over Time (for Subjects Enrolled After Protocol Amendment 2) - PK Analysis Set

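### Figure 14.4-3.4, the only planned display of exposure against effect, appears to plot mean AUC per arm and so loses the within-arm variation, and its 24 h AUC is not defined or listed

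*SAP*

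**What the plan says.** SAP Section 15 lists Figure 14.4-3.4 as "Plot of Mean TXA 24h AUC vs 24h Blood Loss by Method - PK Analysis Set". The only programmer note with it concerns axis margins, and no text section describes the figure or an exposure-response analysis.

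Section 6 gives the design: "Subjects will be randomized in a 1:1:1:1 ratio to receive DepoTXA 400 mg, DepoTXA 800 mg, DepoTXA 1200 mg, or IV TXA", and "Approximately 60 subjects (15 per treatment group) are planned for enrollment". The methods in the title are the haematocrit and haemoglobin calculations of Section 9.8.1 ("Total loss will be calculated separately using two separate methods").

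The note to Table 14.4-1a fixes the reported PK parameters: "Pharmacokinetic parameters to appear on this table are, in order of appearance, AUC(0-infinity) (hr*ng/mL), AUC(0-last) (hr*ng/mL), Global Cmax (ng/mL", followed by the other Cmax and Tmax entries, half-life and lambda_z. No 24 h AUC is among them.

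Efficacy is descriptive (Section 9.8: "No formal statistical hypothesis testing will be performed"), and Section 10 says of the sample size: "The sample size was not based on statistical considerations".

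**The concern.** A plot of exposure against effect is useful when it shows something that a table by dose does not: whether, at the same dose and route, subjects with higher exposure bleed less. Arm means cannot show this. If mean AUC rises with dose, the three DepoTXA points repeat the dose-response with a rescaled horizontal axis. The fourth point, IV TXA, differs in route and formulation as well as in exposure, and plasma AUC need not carry the same meaning for a locally administered depot. A reader who joins the points may see an exposure-response that is really a difference in dose or route, or may miss a relation that exists within arms.

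A second gap concerns the horizontal axis. The plotted exposure measure is not among the parameters that the SAP defines or reports, so the plotted means could not be checked against any table or listing.

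**Working it through.** **1. Is this the only such display?** The planned outputs, side by side:

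- Section 9.10.3 and Figures 14.4-3.1 to 14.4-3.3: concentration against time.
- Tables 14.2-1.1 and 14.2-1.2 and Figures 14.2-9.1 to 14.2-9.3: blood loss by arm and time.
- Figure 14.4-3.4: 24 h AUC against 24 h blood loss.

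Only the last relates the two.

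**2. How many exposure values does it show?** The SAP's own size reproduces: 4 arms × 15 = 60 subjects, of whom 3 × 15 = 45 receive DepoTXA.

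- One mean per arm gives 4 exposure values per method. Over 2 methods that is 4 × 2 = 8 symbols, but the second series repeats the same 4 AUC means. Its blood losses come from the same subjects and the same baseline blood volume.
- The Table 14.1-1 shell enters NA for IV TXA in the PK analysis set row. Taken literally, 3 values per method remain. The PK table shells do carry an IV TXA column, so the SAP is not consistent here.

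**3. What does averaging remove?** Let x be AUC and y blood loss, for subject i in arm a. The joint variation splits as

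Σ(x_ai − x̄)(y_ai − ȳ) = Σ n_a(x̄_a − x̄)(ȳ_a − ȳ) + ΣΣ(x_ai − x̄_a)(y_ai − ȳ_a).

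A plot of arm means shows only the first term, which is tied entirely to assigned dose and route. The second term is the part free of both. In degrees of freedom at planned enrolment:

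| Subjects | Total | Between arms (shown) | Within arms (not shown) |
|---|---|---|---|
| All four arms | 60 − 1 = 59 | 4 − 1 = 3 | 60 − 4 = 56 |
| DepoTXA only | 45 − 1 = 44 | 3 − 1 = 2 | 45 − 3 = 42 |

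These are upper bounds, because Section 8 removes from the PK set subjects with too few samples or with significant deviations.

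**4. Is the 24 h AUC specified?** Section 9.10.2 defines AUC to the last quantifiable concentration and AUC to infinity. The Table 14.4-1a/b list and Listing 16.2-18.2 carry the same two. AUC(0-last) cannot stand in for DepoTXA, whose scheduled sampling runs to 96 h, while IV TXA sampling stops at 24 h (Section 9.10.1). All arms are sampled to 24 h, so AUC(0-24) can be derived from data already planned.

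**5. Does the amendment matter?** The table list in Section 13 says the PK tables are produced separately for subjects before and after the amendment, because the reference time for PK sampling changed. The title of Figure 14.4-3.4 names no such split. Any AUC(0-24) pooled over both groups, as a mean or as individual points, would combine two time references.

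**The case against.** The strongest reply is that the content of the figure is read from its title. The graphic is not in the text available for this review. Figures 14.4-3.1 and 14.4-3.2 say that they are by treatment, while this title says only by method. Four points is therefore an inference, and individual values might be overlaid. This stands as a caveat. However, if individual blood losses were plotted against arm-mean AUC, there would still be only one exposure value per arm.

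Several stronger readings are tempting and are not supported:

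- **That the plot inflates false-positive findings.** A reader might compare how large a correlation must be to differ from zero with four points and with sixty. The SAP plans no correlation, slope or test for this figure. A correlation among arm means and one among individuals are also different quantities. A pooled sixty would again mix IV and depot. Likewise, three unrelated DepoTXA means fall in one given order 1 time in 6 (1/3!), but that applies to any three-dose summary and is not a fault of this plot.
- **That a stated objective goes unanswered.** Section 5.2 asks about "3) a potential dose-related response to DepoTXA at 400, 800, and 1200 mg (33 mg/mL". That is dose-response, which the blood-loss tables and figures by arm address. Exposure-response is not a stated objective. The remark in Section 9.1.1.1 about planning the next phase justifies single imputation of blood loss and does not refer to this figure.
- **That the individual data are lost.** Listings 16.2-6.1.1 and 16.2-6.1.2 give each subject's blood loss, and Listing 16.2-18.1 gives concentrations with actual times. For IV TXA, the listed AUC(0-last) approximates AUC(0-24) when the 24 h sample is quantifiable. Section 4 also allows a post-hoc scatter, labelled as such.

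These replies limit the point to the display and the undefined parameter. They give no reason to prefer means when the paired values are available.

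**Conclusion.** The point holds as a minor improvement. On the natural reading, the one exposure-against-effect display reduces up to 60 subject-level pairs (45 on DepoTXA) to four exposure values, or three on the literal reading of Table 14.1-1. It keeps only the variation that is confounded with dose and route. The likely consequence is an uninformative and possibly misleading descriptive plot. No error rate or planned conclusion is affected, and the pairs can be rebuilt from listings.

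This rests on reading the mean in the title as the arm mean and on planned enrolment as the upper limit of the PK set. The numbers enrolled before and after Amendment 2 are not given, so the number of subjects in each group is unknown. The absence of AUC(0-24) from the definitions, tables and listing does not depend on what the graphic looks like.

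**What to change.** - Retitle Figure 14.4-3.4 and plot each subject's AUC(0-24) against that subject's 24 h blood loss, one panel per method, with the Section 9.1 arm symbols. Show IV TXA separately from the DepoTXA arms. Distinguish subjects enrolled before and after Amendment 2, or give them separate panels, because the PK reference time changed. Overlay arm means if wanted.
- Define AUC(0-24) in Section 9.10.2. The definition should cover a last sample taken off the nominal 24 h (Table 1 of the SAP allows 23 to 25 h) and a last quantifiable concentration before 24 h, since post-dose values below the limit of quantification are set to missing.
- Add AUC(0-24) to Tables 14.4-1a and 14.4-1b and to Listing 16.2-18.2.
- Reconcile the NA for IV TXA in the PK row of Table 14.1-1 with the IV TXA columns of the PK tables, so that it is clear which arms the figure contains.

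The cost is a busier plot and one extra derived parameter. No new data are needed.
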